11.4. Criteria for Endpoints

PASI 50 Responders: Subjects with $\geq 50\%$ improvement in PASI from baseline.

PASI 75 Responders: Subjects with $\geq 75\%$ improvement in PASI from baseline.

PASI 90 Responders: Subjects with $\geq 90\%$ improvement in PASI from baseline.

PASI 100 Responders: Subjects with 100% improvement in PASI from baseline.

11.5. Pharmacokinetic Analyses

Serum guselkumab concentrations over time will be summarized for the guselkumab group. Descriptive statistics, including arithmetic mean, SD, median, interquartile range, minimum, and maximum will be calculated at each sampling timepoint. All concentrations below the lowest quantifiable sample concentration of the assay (BQL) or missing data will be labeled as such in the concentration data listing or statistical analysis system (SAS) dataset. The BQL concentrations will be treated as zero in the summary statistics.

11.6. Immunogenicity Analyses

The incidence and titers of antibodies to guselkumab will be summarized for all subjects who receive at least 1 dose of guselkumab and have appropriate samples for detection of antibodies to guselkumab (ie, subjects with at least 1 sample obtained after their first dose of guselkumab). A listing of subjects who are positive for antibodies to guselkumab will be provided in the clinical study report.

The incidence of neutralizing antibodies (NAbs) to guselkumab will be summarized for subjects who are positive for antibodies to guselkumab and have samples evaluable for NAbs.

11.7. Biomarker Analyses

Biomarker samples outlined in Section 9.4 will be used to assess serum markers, skin gene expression and cellular profiles, [REDACTED] and genetic (DNA) data for biomarker analyses. Biomarker analyses will address the following objectives:

1. To understand the molecular effects of guselkumab and secukinumab.
2. To understand psoriasis.
3. To understand why people may respond differently to guselkumab and secukinumab.
4. [REDACTED]

These analyses are considered exploratory and will be summarized in a separate technical report.

Planned biomarker analyses may be deferred if emerging study data show no likelihood of providing useful scientific information.

Changes in serum/RNA or other biomarkers over time will be summarized by treatment group. Associations between baseline levels and changes from baseline in select biomarkers and clinical response will be explored. RNA analyses will be summarized in separate technical reports.

Results will be presented in a separate report.

11.8. Safety Analyses

Safety data, including but not limited to, AEs, SAEs, infections, serious infections, changes in laboratory assessments, changes in vital signs, changes in electrocardiograms (ECGs), and suicidal ideation and behavior based on eC-SSRS will be summarized. Treatment-emergent AEs will be summarized by treatment group and Medical Dictionary for Regulatory Activities (MedDRA) system organ class and preferred terms.

Safety Definitions

Injection Site Reactions

An injection site reaction is any unfavorable or unintended sign that occurs at an injection site and will be recorded as an AE. Detailed instructions for the evaluation of injection site reactions are in the Trial Center File.

Adverse Events

The verbatim terms used in the eCRF by investigators to identify AEs will be coded using MedDRA. All reported AEs with onset during the treatment phase (ie, treatment-emergent AEs, and AEs that have worsened since baseline) will be included in the analysis.

Summaries, listings, or subject narratives may be provided, as appropriate, for those subjects who die, who discontinue treatment due to an AE, or who experience a severe AE or an SAE.

The following analyses will be used to assess the safety of subjects in the study:

- The incidence and type of AEs.
- The incidence and type of SAEs.
- The incidence and type of infections.
- The incidence and type of reasonably related AEs.
- The incidence and type of injection site reactions.
- The laboratory parameters and change from baseline in laboratory parameters (hematology and chemistry).

In addition, National Cancer Institute-Common Terminology Criteria for Adverse Events (NCI-CTCAE) grades will be used in the summary of laboratory data. A listing of subjects with post-baseline abnormal laboratory results based on NCI-CTCAE grades will also be provided.

Vital Signs

Descriptive statistics of heart rate and blood pressure (systolic and diastolic) values and changes from baseline will be summarized by treatment group.

Electrocardiogram

Electrocardiogram data will be collected at baseline and Weeks 16 and 48. Electrocardiogram data at each visit and change from baseline will be summarized by ECG parameters and by treatment group.

Electronic Columbia-Suicide Severity Rating Scale

Suicide-related thoughts and behaviors based on the eC-SSRS will be summarized descriptively by treatment group.

Anticipated Events

An anticipated event is an AE (serious or non-serious) that commonly occurs as a consequence of the underlying disease or condition under investigation (disease related) or background regimen. For the purposes of this study the event of psoriasis will be considered an anticipated event. Serious adverse events relating to lack of efficacy (eg, events attributed to “psoriasis”) or progression of the disease under study will not be individually unblinded for expedited reporting. These anticipated events will be recorded and reported as outlined in [Attachment 6](#).

11.9. Interim Analysis

No formal interim analysis is planned for this study.

12. ADVERSE EVENT REPORTING

Timely, accurate, and complete reporting and analysis of safety information from clinical studies are crucial for the protection of subjects, investigators, and the sponsor, and are mandated by regulatory agencies worldwide. The sponsor has established Standard Operating Procedures in conformity with regulatory requirements worldwide to ensure appropriate reporting of safety information; all clinical studies conducted by the sponsor or its affiliates will be conducted in accordance with those procedures.

12.1. Definitions

12.1.1. Adverse Event Definitions and Classifications

Adverse Event

An AE is any untoward medical occurrence in a clinical study subject administered a medicinal (investigational or non-investigational) product. An AE does not necessarily have a causal relationship with the treatment. An AE can therefore be any unfavorable and unintended sign (including an abnormal finding), symptom, or disease temporally associated with the use of a medicinal (investigational or non-investigational) product, whether or not related to that medicinal (investigational or non-investigational) product. (Definition per International Conference on Harmonisation [ICH])

This includes any occurrence that is new in onset or aggravated in severity or frequency from the baseline condition, or abnormal results of diagnostic procedures, including laboratory test abnormalities.

Note: The sponsor collects AEs starting with the signing of the ICF (refer to Section [12.3.1](#), All Adverse Events, for time of last AE recording).

Serious Adverse Event

An SAE, based on ICH and European Union Guidelines on Pharmacovigilance for Medicinal Products for Human Use, is any untoward medical occurrence that at any dose:

- Results in death
- Is life-threatening
(The subject was at risk of death at the time of the event. It does not refer to an event that hypothetically might have caused death if it were more severe.)
- Requires inpatient hospitalization or prolongation of existing hospitalization
- Results in persistent or significant disability/incapacity
- Is a congenital anomaly/birth defect
- Is a suspected transmission of any infectious agent via a medicinal product
- Is Medically Important*

*Medical and scientific judgment should be exercised in deciding whether expedited reporting is also appropriate in other situations, such as important medical events that may not be immediately life threatening or result in death or hospitalization but may jeopardize the subject or may require intervention to prevent one of the other outcomes listed in the definition above. These should usually be considered serious.

If a serious and unexpected AE occurs for which there is evidence suggesting a causal relationship between the study drug and the event (eg, death from anaphylaxis), the event must be reported as a serious and unexpected suspected adverse reaction.

Unlisted (Unexpected) Adverse Event/Reference Safety Information

An AE is considered unlisted if the nature or severity is not consistent with the applicable product reference safety information. For guselkumab, the expectedness of an AE will be determined by whether or not it is listed in the Investigator's Brochure. For secukinumab the expectedness of an AE will be determined by whether or not it is listed in the package insert/summary of product characteristics.

Adverse Event Associated With the Use of the Drug

An AE is considered associated with the use of the drug if the attribution is possible, probable, or very likely by the definitions listed in Section 12.1.2, Attribution Definitions.

12.1.2. Attribution Definitions

Not Related

An AE that is not related to the use of the drug.

Doubtful

An AE for which an alternative explanation is more likely, eg, concomitant drug(s), concomitant disease(s), or the relationship in time suggests that a causal relationship is unlikely.

Possible

An AE that might be due to the use of the drug. An alternative explanation, eg, concomitant drug(s), concomitant disease(s), is inconclusive. The relationship in time is reasonable; therefore, the causal relationship cannot be excluded.

Probable

An AE that might be due to the use of the drug. The relationship in time is suggestive (eg, confirmed by dechallenge). An alternative explanation is less likely, eg, concomitant drug(s), concomitant disease(s).

Very Likely

An AE that is listed as a possible adverse reaction and cannot be reasonably explained by an alternative explanation, eg, concomitant drug(s), concomitant disease(s). The relationship in time is very suggestive (eg, it is confirmed by dechallenge and rechallenge).

12.1.3. Severity Criteria

An assessment of severity grade will be made using the following general categorical descriptors:

Mild: Awareness of symptoms that are easily tolerated, causing minimal discomfort and not interfering with everyday activities.

Moderate: Sufficient discomfort is present to cause interference with normal activity.

Severe: Extreme distress, causing significant impairment of functioning or incapacitation. Prevents normal everyday activities.

The investigator should use clinical judgment in assessing the severity of events not directly experienced by the subject (eg, laboratory abnormalities).

12.2. Special Reporting Situations

Safety events of interest on a sponsor study drug that may require expedited reporting or safety evaluation include, but are not limited to:

- Overdose of a sponsor study drug
- Suspected abuse/misuse of a sponsor study drug
- Accidental or occupational exposure to a sponsor study drug
- Medication error involving a sponsor product (with or without subject/patient exposure to the sponsor study drug, eg, name confusion)

Special reporting situations should be recorded in the eCRF. Any special reporting situation that meets the criteria of an SAE should be recorded on the SAE page of the eCRF.

12.3. Procedures

12.3.1. All Adverse Events

All AEs and special reporting situations, whether serious or non-serious, will be reported from the time a signed and dated ICF is obtained until completion of the subject's last study-related procedure, which may include contact for follow-up of safety. Serious adverse events, including those spontaneously reported to the investigator within 12 weeks after the last dose of study drug, must be reported using the SAE Form. The sponsor will evaluate any safety information that is spontaneously reported by an investigator beyond the time frame specified in the protocol.

All events that meet the definition of an SAE will be reported as SAEs, regardless of whether they are protocol-specific assessments. Anticipated events will be recorded and reported as described in [Attachment 6](#).

All AEs, regardless of seriousness, severity, or presumed relationship to study drug, must be recorded using medical terminology in the source document and the eCRF. Whenever possible, diagnoses should be given when signs and symptoms are due to a common etiology (eg, cough, runny nose, sneezing, sore throat, and head congestion should be reported as "upper respiratory infection"). Investigators must record in the eCRF their opinion concerning the relationship of the AE to study therapy. All measures required for AE management must be recorded in the source document and reported according to sponsor instructions.

The sponsor assumes responsibility for appropriate reporting of AEs to the regulatory authorities. The sponsor will also report to the investigator (and the head of the investigational institute where required) all suspected unexpected serious adverse reactions (SUSARs). For anticipated events reported as individual SAEs the sponsor will make a determination of relatedness in addition to and independent of the investigator's assessment. The sponsor will periodically evaluate the accumulating data and, when there is sufficient evidence and the sponsor has determined there is a reasonable possibility that the drug caused a serious anticipated event, they will submit a safety report in narrative format to the investigators (and the head of the investigational institute where required). The investigator (or sponsor where required) must report SUSARs to the appropriate Independent Ethics Committee/Institutional Review Board (IEC/IRB) that approved the protocol unless otherwise required and documented by the IEC/IRB. A SUSAR will be reported to regulatory authorities unblinded. Participating investigators and IEC/IRB will receive a blinded SUSAR summary, unless otherwise specified.

Serious adverse events relating to lack of efficacy (eg, events attributed to "psoriasis") or progression of the disease under study will not be individually unblinded for expedited reporting. These anticipated events will be recorded and reported as described in [Attachment 6](#). All SAEs and nonserious AEs that represent any of the following diagnoses or any symptoms associated with the following diagnoses (eg, chest pain, dizziness) must be reported to the sponsor and will require efforts to obtain additional medical records:

- Myocardial infarction.
- Stroke.
- Cardiovascular death.
- Unstable angina.
- Coronary revascularization (percutaneous coronary intervention or coronary artery bypass graft surgery).
- Transient ischemic attack.
- Venous and peripheral arterial vascular thrombotic events (ie, deep vein thrombosis and pulmonary embolism).
- Congestive heart failure.
- Cardiac arrhythmia.
- Syncope of a cardiovascular origin.
- Severe/accelerated hypertension leading to hospitalization.

If the event is an SAE, the procedures outlined in Section 12.3.2, Serious Adverse Events, should be followed. If the event is a nonserious AE, procedures outlined in the Trial Center File for nonserious AEs (as described above) should be followed.

For all studies with an outpatient phase, including open-label studies, the subject must be provided with a "wallet (study) card" and instructed to carry this card with them for the duration of the study indicating the following:

- Study number
- Statement, in the local language(s), that the subject is participating in a clinical study
- Investigator's name and 24-hour contact telephone number
- Local sponsor's name and 24-hour contact telephone number (for medical staff only)
- Site number
- Subject number
- Any other information that is required to do an emergency breaking of the blind

12.3.2. Serious Adverse Events

All SAEs occurring during the study must be reported to the appropriate sponsor contact person by study-site personnel within 24 hours of their knowledge of the event.

Information regarding SAEs will be transmitted to the sponsor using the SAE Form, which must be completed and reviewed by a physician from the study site, and transmitted to the sponsor within 24 hours. The initial and follow-up reports of an SAE should be made by facsimile (fax).

All SAEs that have not resolved by the end of the study, or that have not resolved upon discontinuation of the subject's participation in the study, must be followed until any of the following occurs:

- The event resolves
- The event stabilizes
- The event returns to baseline, if a baseline value/status is available
- The event can be attributed to agents other than the study drug or to factors unrelated to study conduct
- It becomes unlikely that any additional information can be obtained (subject or health care practitioner refusal to provide additional information, lost to follow-up after demonstration of due diligence with follow-up efforts)

Suspected transmission of an infectious agent by a medicinal product will be reported as an SAE. Any event requiring hospitalization (or prolongation of hospitalization) that occurs during the course of a subject's participation in a study must be reported as an SAE, except hospitalizations for the following:

- Hospitalizations not intended to treat an acute illness or AE (eg, social reasons such as pending placement in long-term care facility)
- Surgery or procedure planned before entry into the study (must be documented in the subject's source documentation). Note: Hospitalizations that were planned before the signing of the ICF, and where the underlying condition for which the hospitalization was planned has not worsened, will not be considered SAEs. Any AE that results in a prolongation of the originally planned hospitalization is to be reported as a new SAE.
- For convenience, the investigator may choose to hospitalize the subject for the duration of the treatment period.

The cause of death of a subject in a study within 12 weeks, whether or not the event is expected or associated with the study drug, is considered an SAE.

12.3.3. Pregnancy

All initial reports of pregnancy in female subjects or partners of male subjects must be reported to the sponsor by the study-site personnel within 24 hours of their knowledge of the event using the appropriate pregnancy notification form. Abnormal pregnancy outcomes (eg, spontaneous abortion, fetal death, stillbirth, congenital anomalies, ectopic pregnancy) are considered SAEs and must be reported using the SAE Form. Any subject who becomes pregnant during the study must be promptly withdrawn from the study and discontinue further study treatment.

Because the effect of the study drug on sperm is unknown, pregnancies in partners of male subjects included in the study will be reported as noted above.

Follow-up information regarding the outcome of the pregnancy and any postnatal sequelae in the infant will be required.

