
FOOTNOTES:
 
a: The screening visit should occur within approximately 4 weeks before the Week 0 visit.
 
b: All Week 48 study procedures should be performed on any subject who terminates the study prior to Week 48, except for collection of serum for biomarkers. If a subject terminates post-Week 48, sites should make every effort to conduct the Week 56 assessments.
 
c: All study procedures and evaluations should be completed before administration of study drug. Assessments for subjects who discontinue study agent administration or withdraw from the study are discussed in Section 10.2.
 
d: Women of childbearing potential must have a negative urine pregnancy test before randomization, before study drug administration, and at all study visits.
 
e: The eC-SSRS should be completed by the subject before any tests, procedures, or other consultations to prevent influencing subject perceptions,
 
f: A tuberculin skin test is additionally required if the QuantiFERON-TB Gold test is not approved/registered in the country in which this study is being conducted.
 
g: Laboratory tests are listed in Section 9.6.
 
h: Subjects must fast (ie, no food or beverages [except water]) for at least 8 hours before blood is drawn for lipid panel. All other visits can be nonfasting.
 
i: All blood samples must be collected before study agent administration at visits when a study agent administration is scheduled. Details will be provided in the Laboratory Manual.
 
j Serum biomarker measurements will include but are not limited to: serum IL-17A, IL-17F, and IL-22. For subjects who discontinue from the study prior to Week 48, serum is not to be collected for measurement of biomarkers.
 
k Biopsy samples for RNA and tissue histology will be collected only from subjects who consent to participate in the optional biopsy substudy. Biopsy samples will be used to assess the cellular and molecular profiles of psoriatic skin lesions at baseline and during treatment.
 
[REDACTED]
 
m: Blood samples for genetic (DNA) analyses will be collected only from subjects who sign a separate consent form to participate in the genetic (DNA) evaluations.
																		

ABBREVIATIONS

BCG	Bacille Calmette-Guérin
BSA	body surface area
CSR	clinical study report
DBL	database lock
ECG	electrocardiogram
eCRF	electronic case report form
eC-SSRS	electronic Columbia-Suicide Severity Rating Scale
eDC	electronic data capture

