9.6. Safety Evaluations

The safety and tolerability of study drugs (guselkumab, secukinumab, or placebo, where appropriate) will be monitored by collecting information on AEs, including injection site and allergic reactions, clinical laboratory tests, physical examinations, vital signs, eC-SSRS questionnaires, electrocardiograms (ECGs), concomitant medication review, and early detection of TB, as specified in the Time and Events Schedule. Serum and/or plasma samples collected for biomarker analyses may also be used to evaluate safety concerns that may arise during or after the study period.

Safety will be monitored through Week 56 or for 12 weeks after the last study drug administration for subjects who discontinue early. Any clinically relevant changes occurring during the study must be recorded on the AE section of the eCRF.

Clinically important abnormalities persisting at the end of the study/early withdrawal may be followed by the investigator until resolution or until a clinically stable endpoint is reached.

The study will include the following evaluations of safety and tolerability according to the timepoints provided in the Time and Events Schedule:

Adverse Events

Adverse events will be reported by the subject for the duration of the study. Adverse events will be followed by the investigator as specified in Section 12, Adverse Event Reporting.

Early Detection of Active Tuberculosis

To aid in the early detection of TB reactivation or new TB infection during study participation, subjects must be evaluated for signs and symptoms of active TB at scheduled visits (refer to Time and Events Schedule) or by telephone contact approximately every 8 to 12 weeks. The following series of questions is suggested for use during the evaluation:

- “Have you had a new cough of >14 days’ duration or a change in a chronic cough?”
- “Have you had any of the following symptoms:
 - Persistent fever?
 - Unintentional weight loss?
 - Night sweats?”
- “Have you had close contact with an individual with active TB?” (If there is uncertainty as to whether a contact should be considered “close,” a physician specializing in TB should be consulted.)

If the evaluation raises suspicion that a subject may have TB reactivation or new TB infection, an immediate and thorough investigation should be undertaken, including, where possible, consultation with a physician specializing in TB.

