10.2. Discontinuation of Study Treatment/Withdrawal from the Study

Discontinuation of Study Treatment

A subject will not be automatically withdrawn from the study if he or she has to discontinue treatment before the end of the treatment regimen.

A subject's study treatment must be discontinued if:

- The investigator believes that for safety reasons or tolerability reasons (eg, AE) it is in the best interest of the subject to discontinue study treatment
- The subject becomes pregnant
- The subject is diagnosed with a malignancy, with the exception of no more than 2 localized basal cell skin cancers that are treated with no evidence of recurrence or residual disease.
- The subject is deemed ineligible according to the following TB screening criteria:
 - A diagnosis of active TB is made.
 - A subject has symptoms suggestive of active TB based on follow-up assessment questions and/or physical examination, or has had recent close contact with a person with active TB, and cannot or will not continue to undergo additional evaluation.

- A subject undergoing evaluation has a chest radiograph with evidence of current active TB and/or a positive QuantiFERON-TB Gold test result and/or an indeterminate QuantiFERON-TB Gold test result on repeat testing (refer to Section 9.6) (and/or a positive tuberculin skin test result in countries in which the QuantiFERON-TB Gold test is not approved/registered or the tuberculin skin test is mandated by local health authorities). Indeterminate QuantiFERON-TB Gold test results should be handled as described in Section 9.6.
- A subject receiving treatment for latent TB discontinues this treatment prematurely or is noncompliant with the therapy.
- The subject initiates a protocol-prohibited medication, eg, for a worsening of his or her psoriasis (unless agreed to by the medical monitor).
- The subject withdraws consent for administration of study drug.
- The subject is unable to adhere to the study visit schedule or comply with protocol requirements.
- The subject develops an allergic reaction such as bronchospasm with wheezing and/or dyspnea requiring ventilatory support, or symptomatic hypotension that occurs following a study drug administration.

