- The subject has a reaction resulting in myalgia and/or arthralgia with fever and/or rash (suggestive of serum sickness and not representative of signs and symptoms of other recognized clinical syndromes) occurring 1 to 14 days after an injection of study drug. These may be accompanied by other events including pruritus, facial, hand, or lip edema, dysphagia, urticaria, sore throat, and/or headache.
- Discontinuation of study treatment should be considered for subjects who report suicidal ideation with intention to act (“4”), suicidal ideation with specific plan and intent (“5”), or a suicide attempt (interrupted suicide attempt, aborted suicide attempt, or preparatory behaviors for making a suicide attempt) on a postbaseline eC SSRS assessment. Discussion of such subjects with the medical monitor or designee is required.
- Discontinuation of study treatment should be considered for subjects who develop a serious or opportunistic infection. Discussion of such subjects with the medical monitor or designee should also be considered.

Subjects who decide to discontinue study drug administration must be interviewed by the investigator to determine if a specific reason for discontinuing study drug can be identified. Subjects should be explicitly asked about the possible contribution of AEs to their decision to discontinue study drug; investigators should confirm that any AE information elicited has been documented. If the subject elects to discontinue study drug due to an AE, the event should be recorded as the reason for study drug discontinuation, even if the investigator’s assessment is that the AE would not require study drug discontinuation. The reason for study drug discontinuation must be documented in the eCRF and in source documents. Study drug assigned to a subject who discontinues may not be assigned to another subject.

If the subject discontinues study treatment before his or her last scheduled injection, he or she should return for the remaining regularly scheduled study visits for at least 12 weeks after receiving the last administration of study drug. For subjects who complete their final study visit prior to Week 48, every effort should be made to conduct the Week 48 assessments as indicated in the Time and Events Schedule. For subjects who discontinue from the study prior to Week 48, serum is not to be collected for measurement of biomarkers.

Withdrawal From the Study

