A subject will be withdrawn from the study for any of the following reasons:

- Lost to follow-up
- Withdrawal of consent
- Death

To ensure access for subject follow-up, study sites should try to obtain both primary and secondary telephone contact numbers from subjects (eg, home, work, and mobile phones), as well as other contact information such as email addresses, and emphasize the importance of follow-up information to the subject, before randomization. For subjects who withdraw from study participation, every effort should be made to conduct the Week 48 assessments, as indicated in the Time and Events Schedule.

If the subject fails to return for study visits (and thus is considered lost to follow-up), study site personnel must make all reasonable efforts to contact the subject to determine the subject's reason for discontinuation/withdrawal before considering the subject to be lost to follow-up. Such efforts should include repeated telephone calls, certified letters, email requests, etc. Measures taken to obtain follow-up information must be documented.

Withdrawal of consent should be a very unusual occurrence in a clinical trial; the investigator should make every effort to maintain good subject relationships to avoid withdrawals of consent. For subjects who truly request withdrawal of consent, it is recommended that the subject withdraw consent in writing; if the subject or the subject's representative refuses to do so or is physically unavailable, the study site should document the reason for the subject's failure to withdraw consent in writing, sign the documentation, and maintain it with the subject's source records. When a subject withdraws before completing the study, the reason for withdrawal is to be documented in the eCRF and in the source document. Study drug assigned to the withdrawn subject may not be assigned to another subject. Subjects who withdraw will not be replaced.

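### Section 12.3.3 withdraws a pregnant subject from the study, whereas Section 10.2 stops only her treatment and keeps her scheduled visits for at least 12 weeks

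*Protocol*

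**What the plan says.** Protocol Section 12.3.3 (Pregnancy) gives a mandatory rule with two separate actions: "Any subject who becomes pregnant during the study must be promptly withdrawn from the study and discontinue further study treatment". It also requires follow-up of the pregnancy outcome and of the infant.

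Protocol Section 10.2 handles the same event differently.

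- Its opening rule: "A subject will not be automatically withdrawn from the study if he or she has to discontinue treatment" early.
- Among the reasons for stopping treatment it lists "The subject becomes pregnant".
- Its closing rule on stopping treatment begins "If the subject discontinues study treatment before his or her last scheduled injection, he or she should return". In full, such a subject "should return for the remaining regularly scheduled study visits for at least 12 weeks after receiving the last administration of study drug".
- Its separate paragraph on leaving the study begins "A subject will be withdrawn from the study for any of the following reasons" and names three: loss to follow-up, withdrawal of consent and death.

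Two other places matter. Section 9.6: "Safety will be monitored through Week 56 or for 12 weeks after the last study drug administration for subjects who discontinue early". Time and Events Schedule, footnote b: "All Week 48 study procedures should be performed on any subject who terminates the study prior to Week 48", biomarker serum excepted.

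**The concern.** Section 12.3.3 names study withdrawal and treatment discontinuation as two actions, so its first half is hard to read as loose wording for stopping the injections. Section 10.2 places pregnancy in the other category. A site with a positive test therefore has two instructions that lead to different follow-up, and nothing in the protocol or SAP reconciles them.

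At stake are the later, repeat assessments in women exposed to study drug during pregnancy: non-serious adverse events, vital signs, eC-SSRS, and any laboratory, drug-concentration or antibody samples due at the dropped visits. There is also a small reporting consequence. SAP Section 4.2 tabulates discontinuation of study agent and premature termination of the study separately, so sites that follow different sections would classify the same event differently.

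**Working it through.** The plan gives no figure to reproduce. The check is a visit count.

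**Inputs**

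- Visits (Time and Events Schedule): Weeks 0, 1, 2, 3, 4, then every 4 weeks to 48, then 56.
- Injections (same schedule): every visit from Week 0 to Week 44. In the guselkumab arm some are placebo only. The count runs from the last injection of either kind, because sites are blinded and Section 9.6 counts placebo among the study drugs.
- Pregnancy testing (footnote d): at every visit and before dosing. If the test is positive at week *v*, the last injection is the one at the previous injection visit, *p*.
- Follow-up rule (Section 10.2): remaining scheduled visits for at least 12 weeks after *p*.

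**Formula**

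The 12-week mark is *p* + 12. The final visit needed is the first scheduled visit at or after that mark. Visits at risk are those after *v*, up to and including that final visit.

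| Detected at week *v* | Last injection *p* | Mark *p* + 12 | Visits at risk | Count | Weeks from *v* to mark |
|---|---|---|---|---|---|
| 1 | 0 | 12 | 2, 3, 4, 8, 12 | 5 | 11 |
| 2 | 1 | 13 | 3, 4, 8, 12, 16 | 5 (or 4) | 11 |
| 3 | 2 | 14 | 4, 8, 12, 16 | 4 | 11 |
| 4 | 3 | 15 | 8, 12, 16 | 3 | 11 |
| 8 to 40 | *v* − 4 | *v* + 8 | *v* + 4, *v* + 8 | 2 | 8 |
| 44 | 40 | 52 | 48, 56 | 2 | 8 |

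*Week 2 and the visit window.* Section 7 allows ±7 days after Week 4 and through Week 44. A Week 12 visit held 7 days late falls at 12 + 1 = 13 weeks and meets the mark, which leaves 4 visits (3, 4, 8, 12). The same shift does not help for detection at Week 3, because 13 < 14.

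*Week 48.* Detection there is not counted. All injections have been given, so the return rule in 10.2 does not apply.

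**Timing of the last scheduled assessment**

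If the exit set is done at detection, it falls *v* − *p* after the last injection: 1 week for Weeks 1 to 4, and 4 weeks for Weeks 8 to 44. Section 10.2 puts the last visit at 12 weeks or more.

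**Example**

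Positive test at Week 20, last injection at Week 16.

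- Section 10.2: visits at Weeks 24 and 28, with the Week 48 assessments at the final visit. That visit is 28 − 16 = 12 weeks after the injection.
- Section 12.3.3 with footnote b: the exit set can be done at Week 20, which is 20 − 16 = 4 weeks after it.

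The exit set includes the routine safety assessments plus physical examination and ECG. What is lost is the repetition at Weeks 24 and 28, including the Week 24 hematology and chemistry and the Week 28 drug-concentration and antibody samples.

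**What remains after withdrawal**

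- Pregnancy and infant outcome (12.3.3).
- SAE reporting and follow-up (12.3.1, 12.3.2).
- The exit assessments (footnote b, 10.2).
- A final serum sample (9.3).
- Concomitant-therapy recording to 12 weeks after the last dose (Section 8).
- Possible safety contact (12.3.1).
- On its face, the 12-week monitoring in 9.6.

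**The case against.** The best defence is precedence. Section 10.2 says only that withdrawal is not automatic, its list of withdrawal reasons is not stated to be exclusive, and its return rule is a *should*. Section 12.3.3 is the section devoted to pregnancy and says *must*. A site could put specific over general and mandatory over advisory, withdraw the subject, and breach no *must* in 10.2.

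Part of this stands. A reader might infer a deadlock in which every choice breaches a mandatory rule, and the documents do not support that, because the return rule is advisory. But the precedence itself is stated nowhere. Section 10.2 also names pregnancy specifically and assigns it to treatment discontinuation. A site that withdraws the subject still departs from the follow-up that 10.2 sets out.

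A reader might also infer that safety follow-up of these women stops at withdrawal. The documents do not support that either. Section 9.6 covers subjects who discontinue early without excluding those who leave the study, and outcome, SAE and exit procedures continue.

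A third tempting reading is an effect on the primary result. Each subject moves an arm's response rate by at most 1/520 = 0.19 percentage points. The documents give no expected number of pregnancies, and they require contraception.

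The precision of the counts is open to fair criticism. They use nominal dates, detection at a scheduled visit and an exit set on the same day. A pregnancy can come to light between visits, and the visit window changes the Week 2 count.

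Finally, the conflict could be removed the other way, by adding pregnancy to the withdrawal reasons in 10.2. That choice belongs to the sponsor, but it would give up the scheduled visits that 10.2 now foresees for these women.

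**Conclusion.** The inconsistency is real, lies in current operative text, and is minor. The mismatch in wording is certain; the loss of visits is only possible. It depends on the site following 12.3.3, on the exit set being done at or near detection (footnote b does not fix its timing), and on how much monitoring is still done under 9.6. On those assumptions the size is typically 2 scheduled visits per affected subject, and about 3 to 5 for detection in Weeks 1 to 4. The finding concerns the clarity and completeness of safety follow-up in a few subjects. It does not bear on the efficacy conclusions.

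**What to change.** Replace the withdrawal sentence in Protocol Section 12.3.3 with: *A subject who becomes pregnant must promptly discontinue study treatment and be followed as in Section 10.2, with safety follow-up for at least 12 weeks after the last administration (Section 9.6) in addition to pregnancy-outcome follow-up.*

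The cost is one sentence of amendment wording. It adds no visit beyond those already foreseen in Sections 10.2 and 9.6.
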